10.5 Adverse Event Reporting

10.5.1 Non-Serious Events

Non-serious AEs should be reported from the day of first IMP administration until 42 days after the last IMP administration. Non-serious AEs occurring between signing the ICF and the first IMP administration must be recorded as medical history.

10.5.2 Serious Adverse Events

Serious AEs should be reported from signing the ICF until 42 days after the last IMP administration.

10.5.3 Adverse Events during Follow-up

From 42 days after the last IMP dose and until the end of the trial, only SAEs at least possibly related to naxitamab, new onset of secondary malignancies and autoimmune diseases (irrespective of seriousness) regardless of causality should be reported (within 24 hours of knowledge).

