7.2.1 Treatment

[figure not shown]
Each treatment cycle is 21 days. Patients will receive irinotecan 50 mg/m²/day IV and temozolomide 100 mg/m²/day orally (both on Days 1-5) in combination with naxitamab 2.25 mg/kg/day IV (Days 2, 4, 8 and 10) (total 9 mg/kg per cycle), and GM-CSF 250 μ g/m²/day sc, (Days 6-10). Patients will receive up to 18 IT cycles after enrollment. Naxitamab and GM-CSF will be given for at least 8 cycles.

Patients who discontinue IT due to unacceptable toxicity will be offered treatment with naxitamab + GM-CSF alone. The treatment will be administered in 28-days cycles with naxitamab 3.0 mg/kg/infusion at Days 1, 3 and 5 and GM-CSF 250 μ g/m²/day for 5 days from Days -4 to 0, and at 500 μ g/m²/day for 5 days from Day 1 to Day 5. The total number of naxitamab treatment cycles will be at least 8 cycles (including the cycles given in the HITS regimen).

Patients who discontinue GM-CSF due to unacceptable toxicity should continue naxitamab treatment.

Patients achieving a CR or PR (both patients receiving HITS or naxitamab + GM-CSF alone) should receive 8 naxitamab cycles or 5 additional naxitamab cycles following the objective response, whichever provides the longest treatment with naxitamab. Patients who have achieved a MR or SD at completion of the 8 cycles (both patients receiving HITS or naxitamab + GM-CSF alone) may receive naxitamab + GM-CSF consolidation treatment for 5 cycles administered at every 6 weeks (in the HITS regimen) or 8 weeks (in the naxitamab + GM-CSF alone regimen). The total number naxitamab cycles to be administered includes the treatment cycles administered in the HITS regimen.

Figure 1 Trial design

*each cycle is 21 days, ** each cycle is 28 days

¹Patients achieving a CR or PR should receive at least 8 naxitamab cycles or 5 additional naxitamab cycles following the objective response, whichever provides the longest treatment with naxitamab

² Patients should receive at least 8 cycles of naxitamab + GM-CSF including the cycles in the HITS regimen

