7.8 Follow-up

EOT assessments should take place minimum 6 weeks (up to 10 weeks) after last treatment. If treatment is discontinued due to PD, planned initiation of new anti-NB treatment prohibited as per protocol, withdrawal from the trial or investigator judges it warranted due to medical reasons/non-compliance, the patient should be called for EOT visit as soon as possible and before initiation of new anti-NB treatment. The patients should subsequently be followed for safety and new anti-cancer therapy for a total of 6 weeks after last treatment (see flowchart in Section 3 and treatment discontinuation criteria in Section 7.12).

After EOT, a long-term FU period will start. The patient will attend long-term FU visits approximately every 4 months for up to 2 years after EOT.

The investigator will perform response assessments (if the patient has not experienced PD) (see Section 3, 9.1.1, 9.1.2 and [Appendix 2](#)), report death and PD (as applicable) and collect information on SAEs ongoing at EOT visit, new SAEs at least possibly related to naxitamab treatment, secondary malignancies, and autoimmune diseases. Furthermore, new anti-cancer therapy should be collected as concomitant medication. Please refer to flowcharts in Section 3 and [Appendix 2](#).

Trial period completion is defined as when the patient has completed the final scheduled visit (long-term FU visit 2 years after EOT).

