8 TREATMENTS

8.1 Investigational Medicinal Products (IMPs)

For this trial, Y-mAbs will provide naxitamab, GM-CSF, irinotecan and temozolomide. All 4 products are classified as IMPs. The IMPs provided must be used solely for this trial as described in this protocol and for no other purpose. For further information on naxitamab, GM-CSF and IT refer to the IB and current summary of product characteristics (SmPCs). A summary of the IMPs is provided in [Table 3](#).

No other medicinal products or auxiliary supplies will be provided by Y-mAbs.

Table 3 IMPs provided by Y-mAbs

IMP:	Irinotecan	Temozolomide	Sargramostim (GM-CSF)	Naxitamab
Route:	IV infusion	Orally	Sc	IV infusion
Dosing instruction:	Days 1-5 50 mg/m ² /day	Days 1-5 100 mg/m ² /day	Days 6-10 ¹ 250 µg/m ² /day ¹	Days 2, 4, 8 and 10 ¹ 2.25 mg/kg/day ¹
Pharmaceutical form:	Solution for infusion	Capsules	Lyophilized 250 µg single use vial	Solution for infusion
Unit strength	20 mg/mL	5, 20 and 100 mg	250 µg/vial	4 mg/mL

¹ Please refer to [Appendix 2](#) for dosing days and dose for treatment of patients who discontinue IT treatment

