10.5.4 Adverse Events with Onset after End of Trial

If the Investigator becomes aware of an SAE after End of Trial with a suspected causal relationship to the IMPs, it should immediately be reported to Sponsor (see contact details in Section 10.7.1)

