10.5.11 Relationship to Investigational Medicinal Product

The Investigator must assess whether the event is related to the IMPs. A suspected adverse drug reaction is defined as one in which there is a reasonable possibility that one of the IMPs caused the AE. Relatedness must be assessed and reported from the first time the AE is being reported. When assessing the causal relationship of an AE to the IMPs, the following should be taken into consideration:

Not related (unlikely)

The AE is not related to any of the IMPs, which means the AE:

- Does not follow a reasonable temporal sequence from IMP administration
- Is readily explained by the patient's clinical state or by other modes of therapy administered to the patient
- Is clearly not related to the IMP

Possibly Related

The AE follows a reasonable temporal sequence from IMP administration but could have been produced by the patient's clinical state, medical history, or the trial procedures/conditions.

Alternative etiology should be provided for all AEs assessed as possibly related to IMPs.

Probably Related

The AE is probably related to one or more of the IMPs, which means the AE:

- Follows a reasonable temporal sequence from IMP administration
- Abates spontaneously upon discontinuation of the relevant IMP(s) (de-challenge) without any curative treatment
- Is confirmed by reappearance of the same reaction on repeat exposure (re-challenge) (if applicable)
- Cannot be reasonably explained by the known characteristics of the patient's clinical state or medical history

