10.9 Reporting of SUSARs

Sponsor will ensure that all relevant information about Suspected Unexpected Serious Adverse Reactions (SUSARs) is reported to regulatory authorities in accordance with regulatory requirements.

The Contract Research Organization (CRO) appointed by Sponsor will notify Investigators of SUSARs in accordance with local requirements. Furthermore, Investigators will be informed of any trial-related SAEs that may warrant a change in any trial procedure. The CRO appointed by Sponsor will inform the Institutional Review Boards (IRBs)/Independent Ethics Committees (IECs) of SUSARs in accordance with local requirement, unless locally this is an obligation of the Investigator.

The Sponsor assessment of expectedness for naxitamab will be performed according to the current version of the IB. For IT and GM-CSF the applicable reference documents will be used.

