12.5.1 Adverse events

AE data will be presented descriptively in summary tables and listings. AEs will be regarded as Treatment-Emergent AEs (TEAEs) if they occur after start of first IMP administration.

An infusion/administration related TEAE is an AE that occurs on a day of IMP administration (after start of IMP administration) and is considered related to the IMP treatment.

An infusion related hypersensitivity TEAE is an AE that match a selected list of hypersensitivity terms based on reported preferred terms (including the MedDRA SMQ narrow scopes of anaphylactic reaction, angioedema, hypersensitivity and severe cutaneous reaction), that occurs on a day of naxitamab infusion (after the infusion start) or the day after a naxitamab infusion irrespectively of relatedness to naxitamab.

AEs with onset during the pre- and post-treatment period will be listed. AEs with onset during the on-treatment period will be summarized as follows: summaries of AEs will be presented for all TEAEs, IMP-related TEAEs, CTCAE Grade 3 or higher TEAEs, IMP-related CTCAE Grade 3 or higher TEAEs, infusion/administration-related TEAEs, infusion-related hypersensitivity TEAEs, SAEs, IMP-related SAEs, CTCAE Grade 3 or higher SAEs, IMP-related CTCAE Grade 3 or higher SAEs, TEAEs leading to treatment discontinuation, AEs leading to death.

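### During long-term follow-up, a new SAE attributed solely to irinotecan, temozolomide or GM-CSF is not requested unless it is a secondary malignancy or autoimmune disease, although all three are IMPs

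*Combined protocol and SAP*

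**What the plan says.** Section 8.1 is explicit about the products: "All 4 products are classified as IMPs". They are naxitamab, GM-CSF, irinotecan and temozolomide.

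The scope of new SAE collection then changes with time:

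- **Consent to 42 days after the last IMP dose (10.5.2):** every SAE, whatever its cause.
- **After that, to the end of the trial (10.5.3):** "From 42 days after the last IMP dose and until the end of the trial, only SAEs at least possibly related to naxitamab". The same sentence adds new secondary malignancies and autoimmune diseases, regardless of seriousness and causality.
- **After End of Trial (10.5.4):** "If the Investigator becomes aware of an SAE after End of Trial with a suspected causal relationship to the IMPs", it is to be reported. There is no restriction to naxitamab.

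The middle rule is not a slip in one sentence. Section 7.8 asks at follow-up visits for "new SAEs at least possibly related to naxitamab treatment, secondary malignancies, and autoimmune diseases", together with death, progression, SAEs ongoing at EOT and new anti-cancer therapy. Table 1 footnote 5 and Appendix 2 (Table 12) footnote 3 say the same.

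On the analysis side, 12.5 opens the post-treatment period at day 43 after the last IMP dose, and 12.5.1 states: "AEs with onset during the pre- and post-treatment period will be listed". The on-treatment summaries in 12.5.1 include a category for IMP-related SAEs.

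**The concern.** The secondary objective (5.2) is the efficacy and safety of the four-drug combination. Section 4.3.8 gives long-term efficacy and safety of naxitamab with IT as the purpose of the 2-year follow-up. A collection rule tied to one of the four products is narrower than either statement, and the protocol gives no reason for it.

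The sequence is also uneven. An SAE attributed only to irinotecan falls outside the request while the patient attends scheduled visits about every 4 months, yet comes within scope if the investigator learns of it after End of Trial.

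At stake is the completeness of a descriptive listing and of the sponsor's late safety information. The SAP cannot restore data that were never collected. In 10.9 the sponsor undertakes SUSAR reporting and adds "For IT and GM-CSF the applicable reference documents will be used". Read literally, 10.5.3 does not ask sites for a late event of that kind attributed solely to those products.

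**Working it through.** The point rests mainly on comparing texts. The plan states no figure here to reproduce.

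**1. What the filter leaves out.** Take a new SAE with onset after day 42 and apply 10.5.3 and 7.8:

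| Late event | Requested? |
|---|---|
| SAE at least possibly related to naxitamab | Yes |
| Secondary malignancy or autoimmune disease, any cause | Yes |
| SAE already ongoing at EOT, any IMP | Yes, followed |
| Death, any cause | Yes, as a death |
| Other new SAE attributed only to irinotecan, temozolomide or GM-CSF | No |

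Only the last row is affected.

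**2. How long the narrower rule applies.** EOT is 6 (up to 10) weeks after last treatment, and follow-up ends 2 years after EOT. Days under the rule = EOT offset + 730 − 42.

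- EOT at 6 weeks: 42 + 730 − 42 = 730 days, of 772 from last dose (730/772 = 95%).
- EOT at 10 weeks: 70 + 730 − 42 = 758 days, of 800 (758/800 = 95%).

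If EOT is brought forward, for example after progression, the period is shorter. This is time under a narrower filter, not time without safety collection.

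**3. Whether naxitamab must be the latest drug.** Section 7.2.1 says "Patients will receive up to 18 IT cycles after enrollment" and sets a minimum of 8 cycles for naxitamab. In the extreme case of 21-day cycles without delay, naxitamab stopped after cycle 8 and IT continued to cycle 18:

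- Last naxitamab: 7 × 21 + 10 = day 157.
- Last IT: 17 × 21 + 5 = day 362.
- Gap: 362 − 157 = 205 days.

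The post-treatment period then opens 43 days after last IT and 205 + 43 = 248 days after last naxitamab. All SAEs within the 205 days are collected, because the 42-day window runs from the last dose of any IMP. The case shows only that the filter can name the less recent drug.

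**4. Size, as an illustration.** The documents give no rate for the affected events. Assume 52 patients, 8 cycles each, EOT at 6 weeks, constant hazard and no other dropout. With h = ln 2 / (median in years), the window runs from a = (24 + 6) weeks = 0.575 years to b = a + 104 weeks = 2.568 years, and person-years = 52 × (e^(−ha) − e^(−hb)) / h. The medians are those cited in 4.1.

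| Time counted | Medians (months) | Person-years |
|---|---|---|
| Alive (OS) | 11.0, 16.1, 27.9 | 34.7, 48.1, 65.8 |
| Alive and progression-free (PFS) | 5.7, 6.4, 12.5 | 14.6, 17.5, 39.2 |

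With an assumed 1 to 5 affected events per 100 person-years, the extremes are 0.01 × 14.6 = 0.15 and 0.05 × 65.8 = 3.3 events. The rate has no source in the documents, so this is not an estimate.

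**The case against.** The strongest reply is that little is lost. Section 10.5.11 sets a low bar for possibly related: a plausible time sequence is enough even where other explanations exist. After a combination regimen, many late events could not be separated from naxitamab and would be reported. Section 10.5.5 also says in general terms that all AEs must be reported. Section 10.5.4 is passive, covering what an investigator happens to learn, whereas 10.5.3 governs scheduled visits. Attribution to IT also weakens once a patient has progressed and started another therapy.

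Most of this stands, and it limits the size of the point. It does not remove it. The low bar depends on individual judgement, and the general sentence in 10.5.5 yields to a specific rule containing the word only.

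Three stronger readings are tempting and are not supported:

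- **That two years of safety data on the other IMPs go uncollected.** Section 7.8 and the footnotes keep deaths, SAEs ongoing at EOT, malignancies, autoimmune diseases and new anti-cancer therapy.
- **That late chemotherapy-related cancers are missed.** Secondary malignancies are reported regardless of causality.
- **That causality is never assessed by product.** Section 10.5.11 is worded jointly ("A suspected adverse drug reaction is defined as one in which there is a reasonable possibility that one of the IMPs caused the AE") but also speaks of the relevant IMP or IMPs, and the eCRF and Clinical AE Report form are not in the documents. A field for each product may already exist.

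**Conclusion.** The inconsistency is real and is stated in four places. From 42 days after the last IMP dose, a new SAE that is neither a secondary malignancy nor an autoimmune disease, and is attributed solely to irinotecan, temozolomide or GM-CSF, is not requested and would be absent from the 12.5.1 post-treatment listing. That does not fit the IMP status of all four products, the wording of 10.5.4 or the purpose given in 4.3.8.

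The consequence is minor. The number of events lost is probably small; the illustration gives fractions of an event up to about three, on an assumed rate and a constant-hazard model. The true number cannot be derived from the documents. Only a descriptive listing and late safety reporting are touched. The primary endpoint, power and on-treatment tables do not change. This is a matter of safety-reporting scope, not a choice of analysis, and the correction is a cheap improvement.

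**What to change.** In 10.5.3, 7.8, Table 1 footnote 5 and Appendix 2 (Table 12) footnote 3, replace the reference to new SAEs at least possibly related to naxitamab with new SAEs at least possibly related to any IMP. Leave the provisions for secondary malignancies, autoimmune diseases and SAEs ongoing at EOT as they are. Collection then matches 10.5.4 and the IMP-related categories in 12.5.1. No new table or analysis is needed.

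The cost is a wording amendment and a few more SAE reports, at visits that already take place about every 4 months. The drawback is weaker attribution after subsequent anti-cancer therapy. That therapy is already recorded during follow-up, so it can be shown beside the event in the listing.

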4 EOT visit should take place 6 (up to 10) weeks after last treatment. If treatment is discontinued due to progressive disease (PD), initiation of new anti-NB treatment prohibited as per protocol, withdrawal from the trial or investigator judges it warranted due to medical reasons/non-compliance, the patient should be called for EOT visit as soon as possible and subsequently be followed for safety and new anti-cancer therapy for 6 weeks after last treatment, and herafter continue in the long-term follow-up.

5 Long-term follow-up (FU) evaluations should take place approximately every 4 months until 2 years after End of Treatment. During long-term FU, information on death, PD, serious adverse events (SAEs) ongoing at EOT, new SAEs at least possibly related to naxitamab, new onset of secondary malignancies and autoimmune diseases should be collected. Furthermore, new anti-cancer therapy should be collected as concomitant medication. (see Section 9.1).

6 Screening imaging and BM examination must be obtained at least 10 calendar days after any prior anti-cancer treatment.

7 Only applicable for D-3 to 0 in cycle 1.

8 Height, weight, physical examination, clinical laboratory assessments, anti-drug antibodies (ADA) and performance test must be performed prior to dosing in each cycle; prior to day (D)1 or at D1.

9 Serum pregnancy test must be done on D-3 prior to gabapentin administration for women of childbearing potential

10 Should only be performed at D15 during C1.

11 Bilateral aspirates and bone marrow (BM) biopsies (2+2), performed at screening and after C2, C4, C8, C13, and EOT. In addition, for patients who achieve a first CR or PR after C4 or a first CR or PR after C8 a confirmatory response assessment should be performed within 4-6 weeks after detection of the overall response. Samples for RTqPCR should be taken at Screening and after C2 and C4. See section section 9.1.2

12 Imaging schedule follows timing of BM biopsies (see #11 above). For a Fluorodeoxyglucose Positron Emission Tomography/ Computed Tomography (FDG PET/CT) scan, the patient must be in fasting state for at least 4 hours prior to the scan. If the patient is not fasting serum glucose determination must be performed prior to the administration of FDG. Please refer to the imaging acquisition guideline for more details.

13 Not to be performed at EOT if the patient discontinue treatment due to PD, provided that PD is documented by scan and/or biopsy. See section [section 9.1.2](#)

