4.3.8 Choice of trial design

Trial 203 is an open label, uncontrolled, multicenter trial. Due to the devastating nature of refractory and relapsed high-risk NB with 10-years OS of less than 15% and the only modest effect of IT treatment alone, a single arm trial design is applied. The primary endpoint ORR is an endpoint accepted for single arm trials by regulatory authorities for efficacy evaluation of anti-cancer therapies^{34, 35}.

The assessment of the primary endpoint after completion of 4 cycles is considered appropriate based on published clinical trials on IT treatment and on completed trials on naxitamab^{17, 18, 21, 22}. The long-term follow-up of 2-years after End of Treatment is to gain data on long-term efficacy and safety of naxitamab in combination with IT.

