5.2 Secondary Objective

To further investigate the efficacy and safety of naxitamab + GM-CSF in combination with IT in patients with high-risk NB with primary refractory disease or in first relapse.

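### During long-term follow-up, a new SAE attributed only to irinotecan, temozolomide or GM-CSF is not reportable unless it is a secondary malignancy or autoimmune disease, so the late safety record of the combination is incomplete

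*Combined protocol and SAP*

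**What the plan says.** Section 8.1 lists naxitamab, GM-CSF, irinotecan and temozolomide and states: "All 4 products are classified as IMPs". The secondary objective in Section 5.2 is "To further investigate the efficacy and safety of naxitamab + GM-CSF in combination with IT". Section 4.3.8 says that the two-year follow-up "is to gain data on long-term efficacy and safety of naxitamab in combination with IT".

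SAE reporting then runs in three periods:

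- **To day 42 after the last dose (Section 10.5.2).** All SAEs, whatever their cause: "Serious AEs should be reported from signing the ICF until 42 days after the last IMP administration".
- **From day 42 to the end of the trial (Section 10.5.3).** The rule becomes "until the end of the trial, only SAEs at least possibly related to naxitamab", plus new secondary malignancies and autoimmune diseases regardless of causality or seriousness. Section 7.8 asks for "new SAEs at least possibly related to naxitamab treatment", and Table 1 footnote 5 for "new SAEs at least possibly related to naxitamab". Table 12 footnote 3 in Appendix 2 has the same scope. Sections 7.8 and both footnotes also collect deaths and SAEs still ongoing at EOT.
- **After End of Trial (Section 10.5.4).** An investigator who becomes aware of an "SAE after End of Trial with a suspected causal relationship to the IMPs" reports it.

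**The concern.** The regimen has four investigational products, and follow-up is meant to describe the late safety of the combination. In the period that follow-up covers, however, a new SAE is screened on its relationship to one product. An SAE that the investigator credits to the chemotherapy or to GM-CSF, and not to naxitamab, falls outside the rule.

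At stake is the completeness of the late safety record. The attribution decides whether the event is reported at all, so a later reader cannot re-examine it. Section 10.9 has the sponsor assess expectedness for IT and GM-CSF as well as for naxitamab, but a late event of this kind need not reach the sponsor for that assessment.

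**Working it through.** The plan states no figure on this point, so there is none to reproduce. The check sets the rules side by side and then measures how long the narrower rule applies.

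**1. What is and is not captured after day 42**

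| New or continuing event | Captured? | Where |
|---|---|---|
| SAE possibly related to naxitamab, alone or jointly with another IMP | Yes | 10.5.3, 7.8, Table 1 fn 5, Table 12 fn 3 |
| Secondary malignancy or autoimmune disease, any cause | Yes | same four places |
| Death | Yes, as a death | 7.8, Table 1 fn 5, Table 12 fn 3 |
| SAE ongoing at EOT | Yes | 7.8, Table 1 fn 5, Table 12 fn 3 |
| Earlier SAE, or treatment-related Grade 3 or higher AE, not yet settled | Followed until resolved, chronic or stable | 10.8 |
| New SAE related only to irinotecan, temozolomide or GM-CSF, neither malignancy nor autoimmune disease | **No** | no section |

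**2. Does another section close the last row?**

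- Section 10.5.5 says that all AEs observed must be reported. It is a general recording instruction, while 10.5.3 is specific to this period and restrictive.
- Section 10.6 requires SAEs within 24 hours but refers back to 10.5 for details.
- Section 10.5.4 uses the wider causality scope, but only for events after End of Trial.

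None of these clearly closes the gap.

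**3. How long the filter applies**

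Inputs: full SAE reporting to day 42 after the last dose (10.5.2); EOT 6 to 10 weeks, or 42 to 70 days, after the last dose, and follow-up to 2 years after EOT, taken as 730 days (both 7.8).

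- End of follow-up: 42 + 730 = day 772, to 70 + 730 = day 800 after the last dose.
- Filtered period: 772 − 42 = 730 days, to 800 − 42 = 758 days.
- Share of time after the last dose: 730/772 = 94.6%, to 758/800 = 94.8%.

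As a share of time since the first dose, the answer depends on treatment length. The filtered period is about 104 to 108 weeks.

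- **8 undelayed 21-day cycles.** Cycle 8 starts on day 1 + 7 × 21 = 148, and its Day 10 is day 157 (22.4 weeks). Follow-up ends at 22.4 + 6 + 104 = 132.4 weeks, to 22.4 + 10 + 104 = 136.4 weeks. Share: 104/132.4 to 108/136.4, about 79%.
- **18 undelayed cycles, last dose on Day 10.** Cycle 18 starts on day 1 + 17 × 21 = 358, and its Day 10 is day 367 (52.4 weeks). Follow-up ends at 162.4 to 166.4 weeks. Share: 104/162.4 to 108/166.4, about 64% to 65%.
- **Last dose at week 70.** Follow-up ends at 180 to 184 weeks. Share: 104/180 to 108/184, about 58% to 59%.

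These are shares of calendar time, not of events. The documents give no rate of late SAEs from which to estimate a number missed.

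**The case against.** The other side has a good deal on its side.

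- **The gap is narrow.** A reader might infer from the word *only* that every late SAE due to chemotherapy or GM-CSF is lost. The documents do not support that. Secondary malignancies and autoimmune diseases are kept whatever the attribution, and deaths and ongoing SAEs are collected. Under Section 10.5.11 an event with reasonable timing can be *possibly related* even if the patient's condition could explain it, so one linked jointly to naxitamab and another IMP is reported. This stands.
- **Sections 10.5.3 and 10.5.4 do not contradict each other.** They govern different periods and different modes: collection at scheduled visits, and notification if the investigator happens to learn of an event. A site can follow both. What remains is a mismatch in scope, with the filter narrower during scheduled follow-up than after it.
- **The secondary objective can still be addressed.** Section 5.2 sets no long-term requirement. Sections 12.5 and 12.5.1 summarise AEs with onset up to 42 days after the last dose and only list later ones, so the planned tables do not change. Follow-up also serves PFS, OS and duration of response. This stands, and only the late safety part is incomplete.
- **Late attribution is confounded.** Section 8.1.4 allows any treatment once all IMPs have stopped, so targeted collection is partly a design choice. That is fair, but it applies equally to SAEs attributed to naxitamab, which are collected. The protocol gives no reason for treating the other three products differently.

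**Conclusion.** The point holds in limited form. From 42 days after the last IMP dose to the end of the trial, one class of event has no reporting route: a new SAE attributed only to irinotecan, temozolomide or GM-CSF that is neither a secondary malignancy nor an autoimmune disease. The late safety record of the combination is incomplete to that extent. On-treatment AE summaries are unaffected; the post-treatment listings are what would lack these events.

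The filter covers about 730 to 758 days per patient, assuming EOT at 6 to 10 weeks and two full years of follow-up. Where EOT is brought forward, for example after progression, or follow-up ends early, the period is shorter. The number of SAEs missed cannot be derived, and the calendar shares above should not be read as a proportion of events lost.

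The conclusion also assumes that sites apply 10.5.3 as the specific rule. If 10.5.5 were meant to override it, sites would hold two incompatible instructions, and the text would still need reconciling. This is an inexpensive wording correction that should be made, not a flaw in the primary analysis.

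**What to change.** In Section 10.5.3, Section 7.8, Table 1 footnote 5 and Table 12 footnote 3, change the causality condition from naxitamab to *any IMP (naxitamab, GM-CSF, irinotecan or temozolomide)*, which matches the scope of Section 10.5.4. Leave the items on deaths, SAEs ongoing at EOT, secondary malignancies and autoimmune diseases as they are.

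If the restriction is deliberate, the alternative is to give the reason in 10.5.3 and narrow the stated purpose of follow-up in 4.3.8.

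The cost is one wording amendment. No visits are added, because follow-up contacts about every 4 months are already planned. Sites will send a few more SAE reports, some confounded by later treatment. New anti-cancer therapy is already recorded during follow-up (Sections 7.8 and 8.4), so that confounding can be examined.
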